6.3.2. Exclusion Criteria

Subjects may not be enrolled into the study if ANY of the following apply:

- Currently pregnant or lactating (subjects who become pregnant during the study will be discontinued).
- Any systemic disease, autoimmune disease, or use of medication, which may interfere with contact lens wear. This may include, but not be limited to, diabetes, hyperthyroidism, recurrent herpes simplex/zoster, Sjögren's syndrome, xerophthalmia, acne rosacea, Stevens-Johnson syndrome, and immunosuppressive diseases or any infectious diseases (e.g. hepatitis, tuberculosis).
- The use of systemic or ocular medications that would contraindicate contact lens wear.

- Entropion, ectropion, extrusions, chalazia, recurrent styes, glaucoma, history of recurrent corneal erosions, aphakia, or moderate or above corneal distortion by keratometry.
- Any previous, or planned, ocular or interocular surgery (e.g., radial keratotomy, photorefractive keratectomy (PRK), laser in situ keratomileusis (LASIK), etc.).
- Any grade 2 or greater slit lamp findings for corneal staining, and any grade 3 or greater slit lamp findings for other abnormalities (e.g., edema, corneal neovascularization, tarsal abnormalities, conjunctival injection) on the ISO 11980 classification scale, any current inflammatory events or events within the last 6 months, or any other ocular abnormality that may contraindicate contact lens wear.
- Any known hypersensitivity or allergic reaction to Biotrue or ClearCare contact lens care solutions
- Any ocular infection, allergy or clinically significant ocular disease (e.g. corneal edema, uveitis, severe keratoconjunctivitis sicca, ocular hypertension), or ocular conditions (e.g. strabismus), which might interfere with the study.
- Any corneal distortion resulting from previous hard or rigid gas permeable contact lens wear.
- Extended wear, monovision or multi-focal contact lens correction.
- Participation in any contact lens or lens care product clinical trial within 30 days prior to study enrollment.
- Any subject where the randomized lens demonstrates a fit that is deemed inappropriate by the investigator, including, but not limited to, the lens being too flat, too steep, have excessive or inadequate movement, and/or insufficient limbal coverage.
- Employee or relative of employees of sponsor or investigational clinic (e.g., Investigator, Coordinator, Technician)

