Significant but non-serious adverse events	Significant but non-serious AEs should include, but not be limited to: 
 — peripheral non-progressive non-infectious ulcers; — all symptomatic corneal infiltrative events; — all cases of corneal staining greater than or equal to grade 3; — a temporary loss of two or more lines of best corrected visual acuity (for greater than or equal to 2 weeks); — cases greater than or equal to grade 2 neovascularization; — any ocular event that necessitates temporary lens discontinuation of greater than or equal to 2 weeks; — lens adhesion or lens binding to the cornea; — significantly distorted corneal topography (significant distortion of keratometry mires or aberrant findings in corneal topography); — any ocular AE that requires the practitioner's intervention, including medication (not including minimal lubrication). 	Notify sponsor as soon as possible, within 5 working days ; IRB and FDA reporting as per requirements
Unanticipated Adverse Device Effect	Unanticipated adverse device effect means any serious adverse effect on health or safety or any life-threatening problem or death caused by, or associated with, a device, if that effect, problem, or death was not previously identified in nature, severity, or degree of incidence in the investigational plan or application (including a supplementary plan or application), or any other unanticipated serious problem associated with a device that relates to the rights, safety, or welfare of subjects.	Notify sponsor immediately ; IRB and FDA reporting as per requirements

Procedures for Handling Adverse Events:

Treatment of an adverse event will depend on its nature and severity. Based on the clinical judgment of the investigator, the subject may be referred to a pre-designated ophthalmologist for treatment. The investigator will attempt to determine whether the reaction is related to the contact lenses or a result of other factors. An Adverse Event Form will be completed for each adverse event. If both eyes are involved, each eye will be counted as one adverse event and Adverse Event information will be completed *for each eye*. Whenever possible, the adverse event will be photo-documented.

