a. Rate your **overall handling of your study lenses:**

Right eye: 0 / 1 / 2 / 3 / 4 / 5 Left eye: 0 / 1 / 2 / 3 / 4 / 5

5	Excellent
4	Very good
3	Good
2	Poor
1	Very poor
0	Unacceptable

Symptoms Questionnaire

How often do your eyes experience the following symptoms during the day **when you wear your study lenses last 7 days?**

	Presence*	Eye*	If yes, please select the frequency*	If yes, please select the severity level*
Discomfort	Yes / No	Right/Left/Both	Rarely / Sometimes / Often / Always	Slight / Moderate / Severe
Excess Tearing	Yes / No	Right/Left/Both	Rarely / Sometimes / Often / Always	Slight / Moderate / Severe
Sensitivity to light	Yes / No	Right/Left/Both	Rarely / Sometimes / Often / Always	Slight / Moderate / Severe
Glare	Yes / No	Right/Left/Both	Rarely / Sometimes / Often / Always	Slight / Moderate / Severe
Halos	Yes / No	Right/Left/Both	Rarely / Sometimes / Often / Always	Slight / Moderate / Severe
Itching	Yes / No	Right/Left/Both	Rarely / Sometimes / Often / Always	Slight / Moderate / Severe
Burning	Yes / No	Right/Left/Both	Rarely / Sometimes / Often / Always	Slight / Moderate / Severe
Blurred Vision	Yes / No	Right/Left/Both	Rarely / Sometimes / Often / Always	Slight / Moderate / Severe
Variability of Vision	Yes / No	Right/Left/Both	Rarely / Sometimes / Often / Always	Slight / Moderate / Severe
Lens Needs cleaning	Yes / No	Right/Left/Both	Rarely / Sometimes / Often / Always	Slight / Moderate / Severe
Other (describe)				

VA/OR with Dispense CL Tab**Visual Acuity and Over-refraction with Dispensed Contact Lens**

	VA with Dispensed Lens (logMar)	Spherical Over-Refraction (D)	VA with Over-Refraction (logMar)
OD			
OS			
OU		n/a	n/a

Is VA with Dispensed Lens on this visit 0.2 logMar worse than initial visit BCVA? Yes No

If "Yes", which eye? OD OS OU

If "Yes", describe the causes of visual acuity change: _____

In the case of visual acuity is reduced by ≥ 0.2 LogMAR, a follow up visit should be scheduled **within 3 days** of the event. If the visual acuity loss persists at follow up, ongoing follow up visits should be scheduled **within 3 days until the visual acuity loss has resolved** or the Investigator determines the condition is stable.

If "Yes", is this VA change greater or equal to 14 days? Yes No (If yes, file Adverse Event Form)

Replacement Lenses

Any new study lens dispensed since last visit without parameter change? Yes No

If yes, OD OS OU

Primary Reason for the Lens Re-dispense: _____

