High probability of sterile infiltrative keratitis	One or more corneal stromal infiltrates the largest of which is 1mm or less in size, and all of the following: outside central 6mm; minimal or no anterior chamber reaction, no mucopurulent discharge; mild or no pain.

Severity of corneal infiltrates on 5-point scale

0 = none	no infiltrates
1 = trace	single or multiple epithelial infiltrates < 1 mm in diameter
2 = mild	Single or multiple epithelial infiltrates \geq 1 mm and $<$ 2 mm in diameter
3 = moderate	Multiple infiltrates \geq 2 mm and $<$ 3 mm in diameter
4 = severe	Multiple dense infiltrates \geq 3 mm in diameter

m. Other complications/Findings

Record other findings (ie, pinguecula) on a 5-point scale and its description. List all report.

OD: 0 / 1 / 2 / 3 / 4

OS: 0 / 1 / 2 / 3 / 4

NOTE

0 = none	no other significant biomicroscopic findings
1 = trace	minimal findings such as a tear film abnormality (debris or low tear break up time)
2 = mild	mild findings such as: lens adhesion
3 = moderate	significant findings e. iritis with minimal cells or flare f. conjunctivitis or EKC
4 = severe	severe findings such as: a. iritis with marked cells and/or flare b. corneal or conjunctival infection c. corneal ulcer d. recurrent erosion

VA / Refraction / Keratometry Tab**Sphero-cylindrical Manifest Refraction and Best Corrected Visual Acuity**

	Sphero-cylindrical Manifest Refraction			Sphero-cylindrical VA (BCVA)
	Sph (D)	Cyl (D)	Axis (°)	LogMar
OD		(-)		
OS		(-)		
OU	n/a	n/a	n/a	

Best Sphere Refraction and Visual Acuity

	Best Sphere Refraction	Best Sphere VA
	Sph (D)	LogMar
OD		
OS		
OU	n/a	

Is BCVA on this visit 0.2 logMar worse than initial visit BCVA? Yes NoIf "Yes", which eye? OD OS OU

If "Yes", describe the causes of visual acuity change: _____

In the case of visual acuity is reduced by ≥ 0.2 LogMAR, a follow up visit should be scheduled **within 3 days** of the event. If the visual acuity loss persists at follow up, ongoing follow up visits should be scheduled **within 3 days until the visual acuity loss has resolved** or the Investigator determines the condition is stable.

If "Yes", is this VA change greater or equal to 14 days? Yes No (If yes, file Adverse Event Form)

Keratometry

	K readings			Corneal Cylinder	
	Flat (D)	Steep (D)	Meridian of Steep Power	Cyl (D)	Axis (°)
OD				(-)	
OS				(-)	

Redisperse Tab

Randomization Group: A / B / C / D

Study Lens Type: Q / V

Care Solution: B / C

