Investigator Printed name of the signer _____

Signature _____

Adverse Event Form

CONFIDENTIAL

84

Adverse Event Form

Subject ID: _____

Date: _____ (MM/DD/ YYYY)

Time: _____ (HH:MM, 24h)

Principal Investigator: _____

Clinical Investigator: _____

Indicate Visit: Baseline / Day 7 / Day 14 / Day 30 / Day 60 / Day 91 /
 Other (please explain the time in investigation from dispensing _____)

Date of Dispensing: _____

Type of Report: Initial AE AE Follow-up (Number of Days following the initial AE Visit: _____)

Adverse events should be differentiated into device related and non-device related. Any corneal infiltrate, ulcer, neovascularization, etc. shall be presumed to be device related unless the case history clearly indicates some other origin. All corneal ulcers shall be recorded in the study report.

Type of Adverse Event: _____

Classification	Definition and condition	Reporting
Serious Adverse Events (SAE)	
Serious Adverse Device Events are those events that result in, or have potential to cause, either permanent impairment of an ocular function or damage to an ocular structure, and may necessitate medical or surgical intervention.
 
Serious AEs may include any hazardous, sight-threatening conditions occurring after exposure to test article, including but not limited to the following.
 
a) A presumed infectious ulcer (defined as a progressive erosion of the corneal tissue). Signs may include irregular focal infiltrates (> 1 mm); active lesions with raised edges; significant diffuse infiltration; anterior corneal to mid-stromal involvement; erosion with overlying staining; conjunctival and lid edema; anterior chamber reaction (iritis); severe bulbar and limbal redness. Symptoms associated with a presumed infectious ulcer (microbial keratitis) may include pain of rapid onset; severe redness; purulent or mucopurulent discharge; tearing; photophobia. For the purposes of reporting, a corneal ulcer which has any of the following characteristics should be considered in this category:
	
Notify sponsor as soon as possible, within 24 hrs; IRB and FDA reporting as per requirements

CONFIDENTIAL

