	
1) central or paracentral location;
 
2) penetration of Bowman's membrane;
 
3) infiltrate > 2 mm diameter;
 
4) associated with iritis ≥ grade 2;
 
5) associated with any increase in intraocular pressure;
 
6) culture positive for microorganisms;
 
7) increasing size or severity at subsequent visits.
 
b) Any central or paracentral corneal event (such as vascularization) that results in permanent opacification.
 
c) Any serious adverse ophthalmic events including hypopyon and hyphema.
 
d) Any neovascularization within the central 6 mm of the cornea.
 
e) The loss of two or more lines of visual acuity that fail to resolve.
 
f) All cases of iritis.
	
Significant but non-serious adverse events	Significant but non-serious AEs should include, but not be limited to: 
 — peripheral non-progressive non-infectious ulcers; — all symptomatic corneal infiltrative events; — all cases of corneal staining greater than or equal to grade 3; — a temporary loss of ten or more letters of best spectacle corrected visual acuity (for greater than or equal to 2 weeks); — cases greater than or equal to grade 2 neovascularization; — any ocular event that necessitates temporary lens discontinuation of greater than or equal to 2 weeks; — lens adhesion or lens binding to the cornea; — significantly distorted corneal topography (significant distortion of keratometry mires or aberrant findings in corneal topography); — any ocular AE that requires the practitioner's intervention, including medication (not including minimal lubrication). 	Notify sponsor as soon as possible, no later than 10 business days ; IRB and FDA reporting as per requirements
Unanticipated Adverse Device Effects (UADE)	Unanticipated adverse device effect means any serious adverse effect on health or safety or any life-threatening problem or sight-threatening, or death caused by, or associated with, a device, if that effect, problem, or death was not previously identified in nature, severity, or degree of incidence in the investigational plan or application (including a supplementary plan or application), or any other unanticipated serious problem associated with a device that relates to the rights, safety, or welfare of subjects.	Notify sponsor and IRB as soon as possible, but no later than 10 business days, if events that are fatal or life threatening, report immediately ; IRB and FDA

		reporting as per requirements

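### The adverse event tables do not separate grade 2 neovascularization already present at Visit 1 from neovascularization that increased, or lens-acuity filings from loss of best corrected acuity

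*Combined protocol and SAP*

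**What the plan says.** **Neovascularization.** Section 6.3.2 (and the synopsis) excludes "any grade 3 or greater slit lamp findings for other abnormalities (e.g., edema, corneal neovascularization, tarsal abnormalities, conjunctival injection", so grades 0, 1 and 2 may enter. Section 14 and the Adverse Event Form in Appendix 3 list "cases greater than or equal to grade 2 neovascularization" among significant but non-serious events. Neither adds a condition such as new or worsened. The form also states: "Any corneal infiltrate, ulcer, neovascularization, etc. shall be presumed to be device related unless the case history clearly indicates some other origin".

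**Acuity.** Section 14 names "a temporary loss of two or more lines of best corrected visual acuity" lasting at least two weeks. The Adverse Event Form words it as "a temporary loss of ten or more letters of best spectacle corrected visual acuity". The Follow-Up Visit form asks two questions:
- With the lens on: "Is VA with Dispensed Lens on this visit 0.2 logMar worse than initial visit BCVA".
- After lens removal: "Is BCVA on this visit 0.2 logMar worse than initial visit BCVA".

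Each is followed by "is this VA change greater or equal to 14 days", and a yes leads to an Adverse Event Form. Appendix 2 defines best corrected acuity as acuity through the sphero-cylindrical refraction.

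**Reporting.** Ocular adverse events are the first primary outcome (6.1.3). Primary outcomes go into summary tables against the control lens (6.2.2), descriptively and without hypotheses (7). Each affected eye counts as one event, and the final report includes all events whatever their class (14). Section 7 tabulates slit lamp findings by visit and lens group. It gives no split of adverse events by Visit 1 status.

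**The concern.** An adverse event count is normally read as what happened after the lens was dispensed. Two rules here, followed literally, can bring in something else.

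The first admits a finding recorded before any study lens was worn. The second compares lens acuity with spectacle acuity. The test lens is spherical (2.1) and up to 0.75 D of cylinder is eligible (6.3.1), so a lens-versus-spectacle gap can exist from dispensing and simply persist.

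With no hypothesis test, the counts by lens are themselves the result, and the control arm is small. A few such eyes could change how the two lenses appear to compare, and a reader of the table could not tell which eyes they were.

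**Working it through.** There is no plan figure to reproduce. Section 6.3.6 bases enrolment on guidance and states no event rate, power or margin.

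**1. Do the grades overlap?** Inputs: 6.3.2 and section 14.

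| Finding | Eligible grades | Event grades | Overlap |
|---|---|---|---|
| Neovascularization | 0, 1, 2 | 2, 3, 4 | 2 |
| Corneal staining | 0, 1 | 3, 4 | none |

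The overlap exists for neovascularization and not for staining.

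**2. Does anything in the text close it?** The serious tier in section 14 speaks of sight-threatening conditions arising after exposure. The significant tier has no such words.

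**3. Weight of one subject.** Up to 50 test and 25 control subjects (6.3.6) give 100 and 50 eyes. One eye is 1/100 = 1% or 1/50 = 2%. Both eyes are 2/100 = 2% or 4/100 = 2/50 = 4%.

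**4. Chance imbalance in neovascularization.** Prevalence is assumed, and every qualifying eye is assumed filed. Expected unchanged eyes are 100p (test) and 50p (control). The probability is the exact binomial sum over both arms, in either direction.

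| Assumed p | Eyes, test / control | Difference of 4 points or more: independent eyes / both eyes together | Difference above 4 points: independent eyes / both eyes together |
|---|---|---|---|
| 1% | 1 / 0.5 | 5.2% / 21.4% | 1.3% / 3.4% |
| 2% | 2 / 1 | 14.0% / 36.0% | 6.0% / 11.7% |
| 5% | 5 / 2.5 | 34.8% / 56.6% | 22.8% / 33.6% |

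The large drop between the last two columns arises because 4 points is exactly one control subject affected in both eyes (1/25).

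**5. The acuity comparators.** Ten letters = 10 × 0.02 = 0.2 logMAR = two lines, so the thresholds agree and only the comparator differs. Example: best corrected acuity −0.10 and a stable lens acuity of +0.10 from dispensing. The difference is 0.20, so the lens item is met at every visit, while the best-corrected item shows a change of 0.

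**6. How often might a stable gap be filed?** All inputs are assumed: normal error with SD 0.05 to 0.10, correlation 0.5 between readings because they share one baseline reading, and no true change since dispensing. An eye is filed if every reading is 0.20 or more worse.

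| True gap | Two readings | Six readings (every 3 days, days 0–15) |
|---|---|---|
| 0.05 | 0.01–1.8% | 0.00–0.2% |
| 0.10 | 0.4–6.3% | 0.02–1.1% |
| 0.15 | 6.3–16.3% | 1.1–4.7% |

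Six readings correspond more closely to the three-day follow-up printed on the form. At a gap of 0.05 or less the rate is at most 1.8%.

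**The case against.** The strongest replies are these.

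- **Occurrence.** Section 14 defines an adverse event as an undesirable clinical occurrence. A finding graded before dispensing and unchanged may not be one. That is a fair reading, and investigators may adopt it, but the text does not state it.
- **Other safeguards.** The Adverse Event Form has fields for date of occurrence and pre-existing conditions. The presumption of relatedness is rebuttable, and the Medical Monitor reviews device-related events. These may stop some counts. None states a baseline rule.
- **Outside guidance.** Section 14 defers definitions to FDA guidance and an ISO standard that are not in the documents. A baseline rule there cannot be ruled out.
- **Planned tables.** Slit lamp findings by visit should show how many eyes in each arm had grade 2 at Visit 1. That stands, but these are marginal counts. They do not show which eyes increased, and they do not carry into the adverse event tables.
- **Poor lens vision is real.** Visit 1 best corrected acuity is the pre-exposure reference, and poor acuity through a lens is a lens effect. This stands, and it limits the acuity part to a mismatch between passages.
- **Assumed magnitude.** The prevalences, gaps and SDs are not from the documents, and the 4-point threshold is sensitive. This also stands.

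A reader might infer that lens-acuity filings are false events from eyes unchanged since entry. The documents do not support that: such a filing may be a valid report, though of something other than loss of best corrected acuity. Nor do they say that the two kinds of event will be pooled in one row; section 7 gives no adverse event table layout.

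**Conclusion.** The point holds in a limited form and is minor.

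Read literally, the rules allow an eye at grade 2 neovascularization at Visit 1, and unchanged, to be counted in the first primary outcome. Whether any eye will be counted this way is not known. A reader might infer that this biases the comparison towards one lens. It does not follow: section 6.4.3 places the slit lamp examination before randomization, so the expected effect is chance imbalance. One bilateral subject moves the rate by 2 points (test) or 4 points (control). The probabilities in the working are illustrations under assumed prevalences of 1% to 5% and complete filing.

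The lens-acuity item on the Follow-Up form does not match the acuity event in section 14 and the Adverse Event Form, whereas the best-corrected item on the same form does. This mismatch needs no assumption. How many filings it would produce depends on lens-versus-spectacle gaps that the documents do not give.

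**What to change.** Leave all adverse event definitions, filing, notification and follow-up triggers unchanged. Because the study is open-label, write the following into the analysis plan before data are tabulated.

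1. Show neovascularization of grade 2 or above by arm in two lines: increased from that eye's Visit 1 grade, and present at Visit 1 but not increased. Report both, and use the first for the between-lens comparison.
2. Reconcile the lens-acuity item on the Follow-Up form with section 14, the Adverse Event Form and the best-corrected item. Tabulate loss of best corrected acuity from the item that compares it with its own Visit 1 value.
3. Show events filed through the lens-acuity item on a separate line. Mark each by whether the gap was already present in the lens acuity recorded at dispensing.

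The cost is a few table lines and no new data. Visit 1 vascularization grade and dispensing lens acuity are recorded per eye, and the Adverse Event Form already lists baseline lens and best corrected acuity. The downside is that the neovascularization count used for comparison is lower than the count filed, so both must be shown.

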6. DESIGN OF THE CLINICAL INVESTIGATION

6.1. GENERAL

6.1.1. Study Design

This is a three-month, open-label, bilateral, parallel group, randomized, daily wear contact lens dispensing study comparing the Qualis Silicone Hydrogel Soft Contact Lens for Daily Wear with the currently marketed Acuvue Vita (senofilcon C) Monthly Contact Lens (FDA cleared under K160212). Eligible subjects will be examined for baseline evaluation and lens fitting. Up to fifty (50) subjects will wear the test contact lenses and up to twenty-five (25) subjects will wear the control contact lenses. The subjects will undergo standard ophthalmic evaluation for contact lens wear and will be followed for a period of ninety days.

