6.1.3. Study Endpoints

Primary Outcome Measures:

- Ocular adverse events/adverse reactions, and adverse device effects;
- Visual acuity

Secondary Outcome Measures:

- Keratometry changes/Refractive Changes;
- Discontinuations (and their reasons);
- Lens Replacements (and their reasons);
- Device Deficiencies;
- Ocular symptoms, problems and complaints;
- Average lens wear time

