6.2. INVESTIGATIONAL DEVICE AND COMPARATORS

6.2.1. Investigational Device

The investigational device is the Qualis Silicone Hydrogel Soft Contact Lens manufactured from a novel silicone hydrogel material. Refer to section 2.1 of this clinical investigation plan for more detailed information regarding the investigational device.

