7. STATISTICAL CONSIDERATIONS

The CRO will manage data analysis and reporting. Subject characteristics and study conduct summaries will be reported—including tables such as a subject disposition table, demographics and baseline characteristics tables (including age, gender, baseline refraction, lens wear experience), summary table of screen failures by reason, accountability of eyes enrolled, and subjects excluded from key analysis sets.

All descriptive summary statistics will be displayed with n and % for categorical data, and with mean, standard deviation, median, minimum, and maximum for continuous data. The unit will be eye. Tables will be presented by treatment and overall. Slit lamp findings will be presented by all study visits, tabulated by eyes and incidence rate for completed test lens group, completed control lens group, discontinued test lens group and discontinued control eyes group. Primary and secondary outcomes will be analyzed by descriptive statistics only. As such, there are no statistical hypotheses to be tested.

Trend analysis profile will be provided following directions provided in the FDA guidance *Premarket Notification [510(k)] Guidance Document for Class II Daily Wear Contact Lenses*. All participants who meet the eligibility criteria, adhere to the protocol, and successfully complete the full study assessment will be available for the per-protocol analysis. Subjects with missing data will be included in the analysis unless there is some non-response-related reason to exclude them, such as a protocol violation/invalid data. Data from all enrolled subjects will be used for reporting of adverse events or other safety related outcomes.

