In general, an ‘adverse event’ refers to any undesirable clinical occurrence in a subject, whether it is considered to be device-related or not. Adverse events (AE) may be classified as ‘serious adverse events’ or ‘significant adverse events’ as defined below.

Classification	Definition and condition	Reporting
Serious Adverse Events	
Serious AEs are those events that result in, or have potential to cause, either permanent impairment of an ocular function or damage to an ocular structure, and may necessitate medical or surgical intervention.
 
Serious AEs may include any hazardous, sight-threatening conditions occurring after exposure to test article, including but not limited to the following.
 
a) A presumed infectious ulcer (defined as a progressive erosion of the corneal tissue). Signs may include irregular focal infiltrates (> 1 mm); active lesions with raised edges; significant diffuse infiltration; anterior corneal to mid-stromal involvement; erosion with overlying staining; conjunctival and lid edema; anterior chamber reaction (iritis); severe bulbar and limbal redness. Symptoms associated with a presumed infectious ulcer (microbial keratitis) may include pain of rapid onset; severe redness; purulent or mucopurulent discharge; tearing; photophobia. For the purposes of reporting, a corneal ulcer which has any of the following characteristics should be considered in this category:
 
 1) central or paracentral location; 2) penetration of Bowman’s membrane; 3) infiltrate > 2 mm diameter; 4) associated with iritis \geq grade 2; 5) associated with any increase in intraocular pressure; 6) culture positive for microorganisms; 7) increasing size or severity at subsequent visits. 
b) Any central or paracentral corneal event (such as vascularization) that results in permanent opacification.
 
c) Any serious adverse ophthalmic events including hypopyon and hyphema.
 
d) Any neovascularization within the central 6 mm of the cornea.
 
e) The loss of two or more lines of visual acuity that fail to resolve.
 
f) All cases of iritis.
	Notify sponsor as soon as possible, within 24 hrs ; IRB and FDA reporting as per requirements

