The primary purpose of the Medical Monitor is to ensure an independent review all Serious Adverse Events (SAE), device-related Adverse Events and AE related to the safety endpoints. When reviewing SAE and device-related adverse events, the Medical Monitor will report the relationship between the AE and the study device and the study procedure. The results of all events reviewed by the Medical Monitor will be documented.

The Medical Monitor will be [name], who is contracted by Andre Vision and Device Research for this activity.

Device Deficiencies:

A device deficiency is an inadequacy of a medical device with respect to its identity, quality, durability, reliability, safety or performance. All device deficiencies related to the identity, quality, durability, reliability, safety or performance of an investigational medical device is documented throughout the clinical investigation on the Device Deficiency Form (eCRF). All device deficiencies will be reviewed by the Clinical Monitor. If it is determined by the Clinical Monitor and Medical Monitor that the deficiency could have led to a serious adverse device effect, the event will be reported to the IRB as soon as possible, but in no event later than 10 working days after the investigator first learns of the event.

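### Section 14 ties the Device Deficiency Form to the investigational device, so capture of control-lens deficiencies depends on which instruction a site follows

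*Combined protocol and SAP*

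**What the plan says.** Section 6.1.3 lists "Device Deficiencies" among the secondary outcomes and does not confine it to one arm. Section 7 adds: "Tables will be presented by treatment and overall". A control column is therefore planned.

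The device deficiency part of Section 14 opens with a general definition: "A device deficiency is an inadequacy of a medical device with respect to its identity, quality, durability, reliability, safety or performance". The sentence that assigns deficiencies to the form is narrower. It concerns the "safety or performance of an investigational medical device is documented throughout the clinical investigation on the Device Deficiency Form (eCRF". The next sentence is general again: "All device deficiencies will be reviewed by the Clinical Monitor".

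Section 6.2.1 settles which lens carries the label: "The investigational device is the Qualis Silicone Hydrogel Soft Contact Lens manufactured from a novel silicone hydrogel material". Section 6.2.2 treats the Acuvue Vita lens separately, as a cleared comparator.

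**The concern.** The sentence that says whose deficiencies go on the form is narrower than the outcome the form feeds. Taken literally, it places no duty on a site to document a faulty control lens, while the same fault in a test lens must be documented. Where the protocol means both products it has wider terms available, such as study lenses and study products, so the narrower term can fairly be read as deliberate.

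The study is open-label, with at least three sites and five investigators, so each site knows which lens a subject wears and can apply the rule by arm. If sites differ in their reading, a low control count could mean few faults or faults regarded as out of scope, and the planned tables could not tell these apart. The distortion would run against the sponsor's own lens, in a study meant to support substantial equivalence.

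**Working it through.** The plan states no figure for this outcome, so the check is mainly a comparison of texts.

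**Texts pointing to the test lens alone**
- Section 14, documentation sentence: refers to an investigational device.
- Section 6.2.1: that device is the Qualis lens. Section 11 likewise attaches the word investigational to the test lenses.

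**Texts covering both arms**
- Section 6.1.3: outcome listed without restriction. Section 7: tables by arm.
- Section 14, definition and Clinical Monitor review: no restriction by device.
- Table #3 in Section 6.1.4: deficiency reporting in every visit column, marked as applicable, not split by arm.
- Section 6.4.7: deficiency reporting in the routines for Visit 1, Visits 2 to 5 and Visit 6, and in the interim visit for lost or broken lenses.
- Appendix 3, baseline and follow-up forms: one form serves both lens types (Q / V), asks whether there is a deficiency to report, and calls for the deficiency report if so.
- Appendix 3, Device Deficiency Form: has a line for the type of device, but no dedicated line for eye or lot.

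The prompts create a route for control-lens reports, but they do not say which deficiencies are reportable. The one sentence that does so by device is the narrow one.

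**What the discrepancy could do (illustration only).** Let p be the true proportion of subjects with a deficiency, assumed equal in both arms, and c the share of control deficiencies that reach the form. Assume complete capture in the test arm. With the maximum enrolment of 50 test and 25 control subjects:
- expected recorded, test = 50p
- expected recorded, control = 25pc
- spurious difference in recorded proportions = p − pc = p(1 − c)

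| Assumed p | Test | Control, c = 1 | Control, c = 0 | Spurious difference |
|---|---|---|---|---|
| 5% | 2.5 | 1.25 | 0 | 0 to 5 points |
| 10% | 5 | 2.5 | 0 | 0 to 10 points |
| 20% | 10 | 5 | 0 | 0 to 20 points |

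Neither p nor c is in the documents. The last column shows bounds under assumed rates, not an estimate.

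**Denominator.** Section 7 makes the eye the unit, but a deficiency belongs to a lens. With dispensing at baseline, Day 30 and Day 60, scheduled lenses at full enrolment number 50 × 2 × 3 = 300 test and 25 × 2 × 3 = 150 control, before unscheduled replacements.

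**The case against.** The strongest reply is that the plan already captures control lenses. Section 14 states a duty for the investigational device and does not exclude others, and the sentences on either side are general. The schedule, visit routines and shared eCRFs raise the question for every subject. This stands in large part. A reader might infer that the outcome has no valid control column, or that the control count must be zero by rule. The documents do not support either: zero would require every site to disregard the prompts. For the same reason, it would not help to calculate how improbable a zero control count is. That would need an assumed rate and would treat 150 lenses from 25 subjects, with paired eyes, as independent.

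Second, many faults are recorded elsewhere. The follow-up form codes replacement or dispensing reasons, including tears, deposits, bad edges and non-wetting surfaces, by eye and lot for both lenses, and lens replacements are a separate secondary outcome. This also stands. It leaves thinner cover for faults without a listed reason, such as labelling errors, which would fall under the free-text option.

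Third, no inference rests on this outcome. Section 7 is descriptive throughout, and Section 6.2.2 names the primary outcomes alone for comparison with the control. That limits the consequence but does not make unequal capture acceptable in a table laid out by arm.

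A reader might also see the same slant in the serious adverse event text, which mentions "any hazardous, sight-threatening conditions occurring after exposure to test article". That inference fails. The phrase sits in a non-exclusive list of examples, Section 14 requires every adverse event to be documented and reported, and Section 7 uses all enrolled subjects for safety.

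**Conclusion.** The point holds as an internal inconsistency that permits unequal ascertainment. The documentation rule in Section 14 is narrower than the secondary outcome, the by-arm tables, the visit schedule and the eCRF prompts. If some sites follow the rule and others the prompt, control deficiencies will be under-recorded relative to test deficiencies and the comparison will be biased against the test lens. If all sites follow the prompt, no bias arises.

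The direction rests on test-lens faults being captured at least as fully as control-lens faults, which is what the wording favours. The size cannot be determined from the documents. The consequence is confined to one descriptive secondary outcome and is softened by the replacement reasons collected in both arms.

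**What to change.** In Section 14, replace the reference to an investigational medical device with any study lens, test or control. The same sentence could say whether care products are included.

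Tabulate deficiencies by arm with lenses dispensed as the denominator. Lens type and lot can be taken from the dispensing eCRFs through the Subject ID. Adding lens type (Q / V), eye and lot to the Device Deficiency Form would make the link direct when the two eyes have different lots.

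The cost is one amended sentence, optionally three form fields, and a few more forms from control subjects. It is best done prospectively, since control faults that were never written down may not be recoverable later.
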